> 20% of the size of the nested cohort) will be used to validate the model. For univariate analysis non-parametric statistical test assuming unequal variance will be employed given the limited sample size. Unpaired Mann-Whitney 'U' test with Bonferroni correction for multiple testing will be used identify lipids (say, set 'A') that shows significant difference in abundance between controls and cases at a given time point. Paired Mann-Whitney test with Bonferroni correction will be used to identify lipids (say, set 'B') that shows significant change in abundance with disease onset in naive subjects. Molecules (say, set 'C') that shows similar pattern of change with time in all three groups, i.e., subjects that present PCOS at beginning, those that develop PCOS during the study and those who never develop PCOS, will be excluded from further analysis to identify putative biomarkers. Rest of the molecules that are common in both sets (A and B) and shows similar pattern of change associated with disease status will be tested as potential biomarkers related to PCOS. In addition, the correlation between lipidomic signatures and non-PCOS clinical or biochemical parameters (such as, body weight, BMI, WC, body fat, fasting glucose, insulin concentration, liver fibrosis score, etc) will be examined. Receiver operating characteristic (ROC) analysis will be performed to examine the sensitivity and specificity of these candidate biomarkers for PCOS diagnosis. In case, there are significant number of new cases of PCOS in both 2nd and 3rd year, cases up to 2nd year will be used to identify consensus lipidomic changes associated with PCOS as described above. Rest of the cases will be used to prospectively validate PCOS markers through ROC analysis. In addition, the ability of baseline abundance of such molecules to predict PCOS incidence at a later time point will be examined using ROC analysis. This would help to identify a multivariate signature that could help to predict PCOS risk in naive subjects.

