#### 2. Work plan & time schedule:

[figure not shown]
Phase-wise plan of action up to post project activities detailing time schedule milestones may clearly be stated.

Time	Activities/work plan	Percent of total activities
0-6 months	Recruitment of JRF, train the JRF, procure consumables and software for lipidomics, procure consumables for biochemical assays.	5%
12-18 month	Procure consumables etc	
24-30 month	Procure consumables etc	
1-3 month	Recruitment of subjects, clinical evaluation, serum sample collection, biochemical assays and diagnosis	10%
13-15 month	Repeat clinical evaluation, serum sample collection, biochemical assays	10%
25-27 month	Repeat clinical evaluation, serum sample collection, biochemical assays	10%
3-34 month	Lipidomic analysis using mass spectrometry, data analysis	55%
32-36 month	Completion of clinical data analysisand manuscript preparation. Completion of lipidomic data analysis, manuscript submission Completion of the project reports and submission	10%

[figure not shown]

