#### 1.7 Year wise deliverables output (preferably point-wise and quantified):

#### 14. Challenges & constraints:

The exact number of PCOS cases at the beginning of the study may be inadequate. In that case, additional subjects from neighbouring hospitals will be recruited. A validation cohort should also be also included in the study, particularly, in case of cross-sectional analysis. Since this longitudinal study has a nested case-control design, the new cases that are diagnosed at later time points will help to test and validate signatures identified at the beginning. Paired statistical analysis of the time series data would significantly help to weed out spurious associations. This is described in the data mining section below. However, it is desirable to have an independent cohort for validation of the results and we would like to involve other hospitals in study once a set of putative markers are identified through this study. Abundance of different lipid molecules are known differ by orders of magnitude. Particularly, phospholipids are very abundant in serum and may mask other low abundance lipids such as bioactive arachidonic acid metabolites during analysis. In order to address the issue, phospholipids will be depleted by passing samples through commercially available phospholipid-binding resin. Platform to platform variability in analysis is often a challenge in translation. To address the issue, in addition to mass spectrometry-based analysis, lipids will further be analyzed using commercially available kits.

This can help to readily validate putative PCOS biomarkers across multiple centres and translate the results into clinically relevant diagnostic assay. This study also offers the opportunity to monitor these subjects further and evaluate the prognostic potential of lipidomic signatures with respect long-term complications of PCOS.

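### Third-year validation is called prospective, but the decision to hold those cases out and one discovery group both wait on third-year diagnoses, so the label is not secured

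*Protocol*

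**What the plan says.** All of this is in the protocol; no SAP is at hand.

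- **Trigger.** Section 1.4, Data mining, makes the split conditional: "In case, there are significant number of new cases of PCOS in both 2nd and 3rd year". No threshold is given.
- **Discovery set.** If the condition is met, "cases up to 2nd year will be used to identify consensus lipidomic changes associated with PCOS as described above".
- **Procedure referred to.** Set A holds lipids that differ between cases and controls at one time point. Set B holds lipids that change within naive women at disease onset. Set C holds lipids that change alike over time in three groups of women: those with PCOS at entry, "those that develop PCOS during the study and those who never develop PCOS". Set C lipids are dropped. Candidates are lipids in both A and B that were not dropped.
- **Validation.** "Rest of the cases will be used to prospectively validate PCOS markers through ROC analysis".
- **Intent.** Section 14 says that "the new cases that are diagnosed at later time points will help to test and validate signatures identified at the beginning".
- **Timing.** The work plan (sections 2 and 15) repeats the clinical evaluation and sampling at months 13-15 and 25-27. It runs "Lipidomic analysis using mass spectrometry, data analysis" as one block over months 3-34.

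**The concern.** Validation is prospective when the signature, and the decision to test it, are settled before the outcomes used to test it are known. Two of the plan's own rules work against this. The decision to have a validation set depends on a count that exists only after the month 25-27 diagnoses. The procedure that yields the lipid list includes a group that can be filled only with those same diagnoses.

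The third-year split is the only held-out test of new cases within the project. If analysts can choose between holding out and pooling after seeing the third-year data, or can still change the list at that point, a good validation ROC carries less weight than its label suggests.

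**Working it through.** **1. What each step needs.**

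| Step in section 1.4 | Latest information needed |
|---|---|
| Set A, cases up to year 2 against controls at one time point | Month 13-15 visit is enough |
| Set B, paired change at onset, cases up to year 2 | Month 13-15 visit is enough |
| Set C, comparison including never-developers | Month 25-27 diagnoses, read literally |
| Decision to split | Month 25-27 count of new cases |
| Validation ROC | Month 25-27 diagnoses and assays |

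The decision to split and the set C step therefore cannot be completed, as written, before the validation outcomes exist. Sets A and B can.

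**2. How open the trigger is.** The protocol gives 200 subjects (section 1.4) and 6-50% PCOS in cross-sectional Indian studies (section 1.1.1, Table 1; 22.5% is the Mumbai Rotterdam figure). It gives no yearly rate of new cases and no threshold, so both are assumed here.

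- PCOS-free at entry = 200 × (1 − p): 188, 155 and 100 for p = 6%, 22.5% and 50%.
- New cases in year 2 = PCOS-free × r. New cases in year 3 = (PCOS-free − year-2 cases) × r.
- Example with p = 22.5% and r = 3%: 155 × 0.03 = 4.65, then (155 − 4.65) × 0.03 = 4.5.
- P(split) = P(at least k in year 2) × P(at least k in year 3), binomial, years treated as independent.

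| PCOS-free at entry | r = 3%, k = 5 | r = 5%, k = 5 | r = 5%, k = 10 |
|---|---|---|---|
| 188 | 0.43 | 0.91 | 0.19 |
| 155 | 0.23 | 0.77 | 0.05 |
| 100 | 0.03 | 0.29 | 0.001 |

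With 155 women and a 5% rate, moving the threshold from 5 to 10 takes the probability from 0.77 to 0.05. Whether validation happens depends largely on a number the plan does not fix.

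**3. Does third-year status in discovery bias the AUC?** Null simulation: 500 independent lipids with no link to PCOS, year-to-year correlation 0.7, 1,000 runs. The ten lipids that best separate year-2 cases from discovery controls are combined and tested on year-3 cases against never-developers. The true AUC is 0.50. Groups are year-2 cases / year-3 cases / never-developers.

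| Discovery controls | 10/10/130 | 20/20/110 |
|---|---|---|
| Women PCOS-free at the year-2 visit | 0.499 | 0.497 |
| Never-developers, different women in validation | 0.501 | 0.500 |
| Never-developers, same women in validation, year-3 samples | 0.534 | 0.559 |
| Never-developers, same women and same samples | 0.550 | 0.586 |

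The standard deviation over runs in the first column is about 0.095, so the Monte Carlo error of those means is about 0.095/√1000 = 0.003. Inflation appears only when the same never-developers are controls in both steps. A further simulation of that reuse gave 0.51-0.52, so the size depends on the settings.

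**4. The set C step by itself.** 300 null lipids, correlation 0.7, 30 women with PCOS at entry (assumed), the same group sizes, 300 runs each. Set C was taken as a mean change of the same sign in all three groups. Discovery controls were women PCOS-free at year 2, or a separate half of the never-developers. Mean validation AUC was 0.497-0.503 with set C defined by third-year status and 0.499-0.504 with year-2 status. No effect is visible.

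**The case against.** The strongest reply is that the plan can be carried out prospectively. Sets A and B need only data up to year 2. Limiting discovery to cases up to year 2 could imply that the whole procedure is cut there. Section 1.6 places lipidomic and data analysis in the second year, and section 14 expects later cases to test earlier signatures. Freeze dates and thresholds often belong in an SAP. Section 18 calls the project exploratory, and asking for enough cases before running an ROC is sensible. Most of this stands, and it limits the point to what the wording secures. It does not remove the point: the trigger names the third-year count, and an SAP could honour the label only by overriding that text.

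A reader might infer more, in four ways that the documents do not support.

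- **That the signature cannot be fixed in time.** It can; there are ten months between month 15 and month 25.
- **That knowing the count, or the set C step, biases the AUC.** Knowing the count does not itself bias it, and the set C simulation shows no effect.
- **That a useless signature would validate with an AUC of 0.63 to 0.73.** These figures are the expected best of ten independent null lipids: 0.5 + 1.54 × √((n1 + n0 + 1)/(12 × n1 × n0)), with n0 = 150 and n1 = 12, 6 or 4 giving 0.63, 0.69 and 0.73. They assume that lipids are picked by their validation AUC, which nothing in the plan prescribes. Candidates must also pass Bonferroni in sets A and B. At an assumed 5% level, at most 0.05 null lipids are expected in set A alone, so ten are implausible. The figures are at most an illustrative worst case.
- **That no validation is left if the count is too low.** Leave-one-out cross-validation remains, and sections 14, 17 and 19 foresee independent cohorts afterwards. What is lost is the held-out test of new cases within this project.

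**Conclusion.** The point holds in a limited form. The plan describes its third-year test as prospective, but its stated rules let the choice to hold out or pool, and the final lipid list, be settled after the third-year outcomes are known. The risk has three parts: the late choice under an undefined threshold, a list that may still be open when third-year data are visible, and a mild inflation if never-developers are controls in both steps.

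Only the third part has a simulated size: a mean null AUC of 0.51 to 0.59, under independent lipids, a year-to-year correlation of 0.7 and assumed group sizes. It also requires a choice of controls that the protocol does not state. The first two parts depend on conduct and cannot be sized from the documents. The trigger probabilities rest on assumed yearly rates and thresholds. A literal reading of never-developers is assumed as well; if that group were cut at year 2, the trigger problem would remain. The wording should be changed because the correction is cheap and the validation claim depends on it.

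**What to change.** Rewrite the rule in section 1.4, Data mining:

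1. Decide the split without reference to the third-year count.
2. Define the discovery groups by status at the month 13-15 visit: PCOS at entry, PCOS by that visit, PCOS-free through that visit. In the simulation, discovery controls defined this way returned the null AUC to 0.50.
3. Freeze the lipid list, direction, weights and cut-off in a dated file before any month 25-27 diagnosis or assay result is merged.
4. Report the validation ROC on third-year cases with a confidence interval. Fix in advance any minimum count for interpreting it.
5. Label any analysis that pools all cases as exploratory.

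If the sponsor prefers to keep the present rule, delete the word prospectively.

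The cost is protocol wording and one dated file; the existing gap between visits allows it. The downside is that third-year cases are not available to the main discovery step, and with few of them the validation interval may be wide.

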#### **Epidemiology:**

Data on incidence of PCOS is hugely influenced by the definition of PCOS followed in the respective study. PCOS incidence has been reported to vary from 2.2-26% worldwide (1-5). In India, only a handful of epidemiological studies have been reported on PCOS. The following table summarizes results of those studies. Table 1: Summary of Epidemiological Studies on PCOS in India

 Study Design	Location	Sample size	Age range	Incidence (%)	PCOS definition	Non- obese PCOS (%)	Reference
Cross- sectional	Mumbai	778	15-24	22.5 10.7	Rotterdam NIH	71.8%	Joshi B et al Indian Journal of Endocrinology and Metabolism / May-Jun

							2014 / Vol 18   Issue 3
Cross- sectional	Kanchipuram/Chennai	1068	18-24	6	Rotterdam	62%	Bharathi, RV Middle East Fertility Society Journal 22 (2017) 313– 316
Cross- sectional	Bangalore	460	18-45	9.13	Rotterdam	-	R Nidhi et al J Pediatr Adolesc Gynecol 24 (2011) 223e227
Cross- sectional	Dehradun	170	16- 30+	41	NIH	14%	Choudhary A et al. Int J Reprod Contracept Obstet Gynecol. 2017 Nov;6(11):4971-4975
Cross- sectional	Bhopal	500	17-24	8.4	Rotterdam	17%	Gupta M et al. Int J Community Med Public Health. 2018 Jan;5(1):95-100
Cross- sectional	Sevagram	200	15-34	50	Rotterdam	-	Chhabra S J Obstet Gynaecol. 2010 Jan;30(1):41-5.
Cross- sectional	Vellore	126	12-19	18	Rotterdam	-	Balaji, S et al Biomed Res Int. 2015;2015:158951.

As can be seen in the table, PCOS incidence varied widely from 6-50% among different studies. This calls for multi-centre studies involving larger sample size and uniform diagnostic criteria. Few studies (Bharathi, RV et al and Balaji S et al) have indicated higher incidence of PCOS in urban women. While stress and other life-style

related factors may contribute to a higher abundance as suggested in these articles, underreporting in rural set up due to stigma involved with consequences of PCOS may also contribute to this difference. One of the striking features of PCOS in India is that a significant percentage of PCOS patients are non-obese at diagnosis. However, it should be noted that all these studies stratify subjects based on BMI and/or waist circumference. None of them analyzed the total body fat using technologies such as dual energy X-ray absorptiometry (DEXA), which truly represents the adiposity of the subject.

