#### **Study population**

Freshers admitted in MBBS course at IPGME&R and SSKM hospital. We aim to recruit 200 subjects.

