#### **Overview of the Workflow:**

Approximately 200 young adult subjects will be enrolled and examined for PCOS incidence as per Rotterdam criteria in addition to comprehensive physio-clinical, radiological and biochemical evaluation. This exercise will be repeated for all subjects every year.

**Figure 1:** Schematic representation of overall plan of work for identification of early markers of PCOS using serum lipidomics.

Serum samples collected during this exercise will be subjected to lipidomic analysis using Ultra-performance liquid chromatography (UPLC)-electrospray ionization mass spectrometry (ESI-MS) as well as gas chromatography coupled with mass spectrometry (GC-MS). These data will be combined and mined using multivariate statistical analysis to identify features of interest. This will be further subjected to rigorous statistical analysis for robustness of association of signatures with PCOS.

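### ROC accuracy of the candidate lipids is estimated on the women who selected them, and the conditional year-3 validation sets aside cases but no controls, so reported accuracy will be optimistic

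*Protocol*

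**What the plan says.** All of this is in the protocol, section 1.4, Data mining (under Lipidomic Analysis), unless stated otherwise.

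- **Selection.** Set A holds lipids that differ between cases and controls at a given time point (unpaired Mann-Whitney, Bonferroni). Set B holds lipids that change with onset in initially PCOS-free women (paired test, Bonferroni). Set C, lipids with a similar time pattern in prevalent cases, converters and never-cases, is removed. Candidates are common to A and B and outside C.
- **Accuracy.** ROC "analysis will be performed to examine the sensitivity and specificity of these candidate biomarkers for PCOS diagnosis". No separate data set is named. A further ROC uses baseline levels of the same molecules to predict later PCOS, again with no separate data.
- **Hold-out.** It is conditional: "In case, there are significant number of new cases of PCOS in both 2nd and 3rd year", cases up to year 2 are used for discovery. Then: "Rest of the cases will be used to prospectively validate PCOS markers through ROC analysis". No threshold is given and no validation controls are named.
- **Cross-validation.** Iterative leave-one-out follows the PLS-DA/OPLS-DA sentence and is said to validate that model. The number of iterations need only exceed 20% of the nested cohort.
- **Reliance on later cases.** Section 14 says "the new cases that are diagnosed at later time points will help to test and validate signatures identified at the beginning". It calls an independent cohort desirable, and section 19 lists it as a post-project activity.
- **Cohort.** "We aim to recruit 200 subjects" (Study population), and "This exercise will be repeated for all subjects every year" (Overview of the Workflow).

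**The concern.** A lipid enters set A because its case-control Mann-Whitney statistic is extreme in this sample. The AUC is that statistic divided by the number of case-control pairs. Selecting on it and then reporting it in the same women favours lipids whose separation was exaggerated by chance.

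The hold-out does not reliably correct this. Whether it runs can be decided after the new cases have been counted. When it runs, the text gives new cases but does not say which women supply specificity. Year-3 converters were PCOS-free at earlier visits, so they may have served as discovery controls. Set C also needs groups that are fully known only after the last visit.

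Sensitivity and specificity are the figures a reader would use to judge whether the signature could support the screening and diagnostic use described in section 1.3.

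**Working it through.** **Inputs.** The protocol states no target AUC, sensitivity, specificity, alpha, lipid count or expected number of cases, so there is no figure of its own to reproduce. From the document: 200 women. Assumed: two-sided alpha 0.05; 200 or 500 lipids; 20, 40 or 60 cases among the 200 (10%, 20%, 30%). These shares lie inside the range in the Epidemiology section, where "PCOS incidence varied widely from 6-50% among different studies".

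**Step 1. Smallest observed AUC that set A can select.** With AUC = U/(n1·n0), the null standard error is sqrt[(n1+n0+1)/(12·n1·n0)]. The floor is 0.5 + z × SE, with z at 1 − 0.05/(2 × lipids): 3.891 for 500 lipids and 3.662 for 200.

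| Cases, controls | SE | Floor, 500 lipids | Floor, 200 lipids |
|---|---|---|---|
| 60, 140 | 0.0447 | 0.674 | 0.664 |
| 40, 160 | 0.0512 | 0.699 | 0.687 |
| 20, 180 | 0.0682 | 0.765 | 0.750 |

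Worked example for 40 and 160: sqrt(201/76,800) = 0.0512, and 0.5 + 3.891 × 0.0512 = 0.699. No selected lipid can show an AUC below its floor on the selection data in the case direction, whatever its true AUC.

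**Step 2. Simulated optimism.** 500 independent normal lipids, 20 of them truly shifted; set A selection with Bonferroni; score = signed sum of the selected lipids; 200 runs per row. Means are over runs in which at least one lipid was selected. The hold-out columns use 10 new cases. Sets B and C were not modelled.

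| Cases, controls | Shift (SD) | Runs with a selection | Selection data | New cases, reused controls | New cases, new controls | Large independent sample |
|---|---|---|---|---|---|---|
| 20, 180 | 0.3 | 8% | 0.785 | 0.575 | 0.557 | 0.550 |
| 20, 180 | 0.5 | 35% | 0.789 | 0.663 | 0.647 | 0.636 |
| 20, 180 | 0.7 | 92.5% | 0.883 | 0.778 | 0.764 | 0.771 |
| 40, 160 | 0.3 | 20.5% | 0.718 | 0.623 | 0.591 | 0.571 |
| 40, 160 | 0.5 | 88% | 0.811 | 0.720 | 0.695 | 0.703 |
| 40, 160 | 0.7 | 100% | 0.959 | 0.933 | 0.923 | 0.920 |

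Excess of the selection-data AUC over the independent value runs from 0.959 − 0.920 = 0.039 to 0.785 − 0.550 = 0.235. For new cases against reused controls the largest excess is 0.623 − 0.571 = 0.052. With cases and controls both new, the mean returns close to the independent value.

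**Step 3. Does leave-one-out cover this?** No. As written it validates the PLS-DA/OPLS-DA model. The A/B/C selection is a separate univariate route described after it, and the ROC is run on the output of that route. Nothing repeats the selection with a woman left out.

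**Step 4. Why the hold-out needs a stated minimum.** By the Hanley-McNeil standard error at AUC 0.75 with 140 controls, the 95% half-width is about 0.28, 0.20 and 0.14 for 4, 8 and 16 held-out cases (illustrative counts).

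**The case against.** Several points on the other side stand.

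- **The project is exploratory.** Section 18 says so. The main ROC is worded as an examination of candidate markers, section 17 ties impact to later validation in an independent cohort, and section 19 plans that work. A reader might infer that the main ROC is itself presented as validation; the text does not say that. The word *validate* attaches to the PLS-DA model and to later cases.
- **The plan does cross-validate.** A reader might infer that it would report an uncross-validated PLS-DA fit, which can look near perfect on noise. It would not: leave-one-out is specified for that model. The gap is that this step does not reach the A/B/C selection or the ROC.
- **Control reuse is not stated.** The text is silent on validation controls. Year-3 serum from never-PCOS women would be new samples, though from women already seen. The earlier PCOS-free status of year-3 converters breaks independence but need not raise the AUC.
- **Sets B and C are not in the calculation.** Requiring set B as well makes pure-noise candidates unlikely. If the paired test is read as an exact signed-rank test, its smallest two-sided p is 2/2^n. For 500 lipids the limit is 0.05/500 = 0.0001, and n = 14 gives 0.00012 while n = 15 gives 0.00006. With fewer than 15 converters set B would be empty and there would be no candidate to evaluate.
- **The largest optimism is conditional.** The 0.235 arises where only 8% of runs selected anything.

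Fold structure and bootstrap intervals can be left to an analysis plan. The protocol itself, however, fixes which data are used for selection and ROC, the undefined trigger, and a split of cases only.

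**Conclusion.** The concern holds in bounded form. As written, ROC for the candidate lipids gives apparent sensitivity, specificity and AUC, because the same women select the lipids and no step repeats that selection out of sample. Under the stated assumptions (alpha 0.05, 500 lipids, 20 or 40 cases of 200, set A alone, independent normal lipids), the AUC is too high by about 0.04 to 0.24. If the hold-out ran with discovery controls reused, the excess would be at most about 0.05. The direction is secure; the size is not fixed by the document. The year-3 step is weak mainly because its trigger is undefined and validation controls are unspecified. The protocol gives no conversion rate, so whether the step would ever run cannot be judged. This should be fixed, but given the exploratory aim and the planned independent testing it does not invalidate the study.

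**What to change.** 1. Report ROC from out-of-fold predictions, leaving out whole women with all their visits and repeating the full A/B/C selection in each fold. A bootstrap optimism correction that repeats the selection is an acceptable alternative. Treat the baseline-prediction ROC in the same way.
2. If the year-3 hold-out is kept, replace the undefined condition with a minimum number of new cases stated in advance. Before any lipid selection, assign whole women to validation: the year-3 converters with all their samples, and a random set of never-PCOS women. Call the result internal validation.
3. Label any ROC on the selection women as apparent or exploratory.
4. State that the leave-one-out step applies to the PLS-DA/OPLS-DA model only, or extend it to the selection.

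**Cost.** More computing, a somewhat lower reported AUC, and fewer controls for discovery. No new women or assays are needed. The assignment has to be fixed beforehand, because a clean split cannot be recovered once lipids have been chosen.

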#### 15. Work plan & time schedule:

Time	Activities/work plan	Percent c activities	of total
0-6 months	Recruitment of JRF, train the JRF, procure consumables and software for lipidomics, procure consumables for biochemical assays.	5%	
12-18 month	Procure consumables etc		
24-30 month	Procure consumables etc		
1-3 month	Recruitment of subjects, clinical evaluation, serum sample collection, biochemical assays and diagnosis	10%	
13-15 month	Repeat clinical evaluation, serum sample collection, biochemical assays	10%	
25-27 month	Repeat clinical evaluation, serum sample collection, biochemical assays	10%	
3-34 month	Lipidomic analysis using mass spectrometry, data analysis	\$55%	
32-36 month	Completion of clinical data analysisand manuscript preparation. Completion of lipidomic data analysis, manuscript submission Completion of the project reports and submission	10%	

- 16. Output and Translational Outcome of the project: The proposed study aims to identify signatures for early diagnosis of PCOS using serum lipidomics. It also aspires to test the ability of lipidomic signatures to identify PCOS-naive subjects at imminent risk of PCOS development. Currently, there is no reliable biomarker for PCOS diagnosis or risk analysis. Identification of such biomarkers will immensely help patients and clinicians in early diagnosis and timely intervention to ameliorate the long-term complications of PCOS. In addition, identification of subjects at risk may be useful in effective life-style management and/or interventions
- 17. **Likely impacts** (please quantify in case of measurable parameters). Identification of biomarkers of PCOS in this study and subsequent validation in independent cohort would have significant impact on patients and clinicians in terms of screening, diagnosis and therapeutic management of the disease

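### The onset-prediction ROC uses the baseline sample only and fixes no horizon, so 12- and 24-month leads may be pooled and the month 13-15 PCOS-free sample of third-year converters is not a predictor in it

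*Protocol*

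**What the plan says.** The Data mining text in section 1.4 first selects lipids in three steps. Set A holds lipids with a "significant difference in abundance between controls and cases at a given time point". Set B comes from a paired test of change with onset in women who were free of PCOS. Set C holds lipids that change alike over time in women with PCOS at entry, women who develop it and women who do not; these are dropped. The text then adds the prediction step: "the ability of baseline abundance of such molecules to predict PCOS incidence at a later time point will be examined using ROC analysis". This is the only analysis there that takes a sample from before diagnosis as a predictor of later PCOS.

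The Work plan schedules "Recruitment of subjects, clinical evaluation, serum sample collection, biochemical assays and diagnosis" at months 1-3 and "Repeat clinical evaluation, serum sample collection, biochemical assays" at months 13-15 and again at months 25-27. The Overview of the Workflow says of the evaluation, "This exercise will be repeated for all subjects every year", and "Serum samples collected during this exercise will be subjected to lipidomic analysis". Item 16, on translational outcome, hopes to "identify PCOS-naive subjects at imminent risk of PCOS development".

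**The concern.** Three yearly visits give two kinds of converter. A woman first diagnosed at the second visit has one PCOS-free sample, about a year before diagnosis. A woman first diagnosed at the third visit has two, about two years and about one year before. The prediction ROC takes the baseline sample from both.

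Two things follow. First, the outcome is to "predict PCOS incidence at a later time point", with no time point named, so an AUC could combine two lead times and carry no definite horizon. If a lipid changes mainly in the last year before diagnosis, third-year converters will resemble controls at baseline and pull a pooled AUC towards 0.5. Second, the sample from third-year converters that best matches the hope of detecting imminent risk has no place as a predictor. The protocol itself describes its sample size as limited, and converters will be few, so leaving out about half of the available 12-month-lead cases matters.

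**Working it through.** The protocol gives no target AUC, conversion rate or expected number of converters, so there is no figure of its own to reproduce.

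**Lead times (visit windows from the Work plan)**
- Baseline to diagnosis at the second visit: 13 - 3 = 10 to 15 - 1 = 14 months.
- Baseline to diagnosis at the third visit: 25 - 3 = 22 to 27 - 1 = 26 months.
- Second visit to diagnosis at the third: 25 - 15 = 10 to 27 - 13 = 14 months.

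These run to the diagnosis visit. True onset lies somewhere in the preceding year.

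**Number of converters**

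Inputs: 200 recruited (Study population). PCOS at entry is assumed to be 22.5%, the Rotterdam figure of the Mumbai survey in Table 1, with 6% and 50%, the ends of the range the protocol quotes, as limits. Annual conversion *i* is assumed to be 5%, with a range of 2-10%. No dropout and no added subjects.
- PCOS-free at entry: 200 x (1 - 0.225) = 155.
- Second-year converters: 155 x 0.05 = 7.75, leaving 147.25.
- Third-year converters: 147.25 x 0.05 = 7.36, leaving 139.89.
- Total: 15.11.
- Third-year share of all converters: (1 - *i*)/(2 - *i*), which is 0.495, 0.487 and 0.474 at 2%, 5% and 10%.

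**If the two diagnosis visits were pooled**

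Against a common control group, the pooled AUC is the case-weighted mean of the two AUCs. The component AUCs here are illustrative assumptions only.
- 0.80 at 12 months and 0.60 at 24 months: (7.75 x 0.80 + 7.36 x 0.60)/15.11 = 0.70.
- 0.80 at 12 months and 0.50 at 24 months, the no-signal extreme: with an even split, 0.5 x 0.80 + 0.5 x 0.50 = 0.65.

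Neither result describes either horizon.

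**If the visits were analysed separately**

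Under the plan, only second-year converters then give evidence at a 12-month lead. Precision is the Hanley-McNeil standard error at an assumed AUC *A* = 0.75:

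SE² = [A(1 - A) + (c - 1)(Q₁ - A²) + (n - 1)(Q₂ - A²)]/(c n)

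with Q₁ = A/(2 - A) = 0.600, Q₂ = 2A²/(1 + A) = 0.643, *c* cases and *n* controls.

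| 12-month-lead analysis | Cases | Control samples | SE |
|---|---|---|---|
| Baseline sample, second-year converters (as planned) | 7.75 | 147.25 | 0.103 |
| Month 13-15 sample, third-year converters | 7.36 | 139.89 | 0.106 |
| Last PCOS-free sample, all converters | 15.11 | 147.25 + 139.89 = 287.14 | 0.074 |

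The last row treats control samples as independent, although most control women appear twice. Counting only 147.25 controls gives 0.075, so the gain comes from the cases.

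Over 6-50% PCOS at entry and 2-10% conversion, the 12-month-lead cases rise from 2.0-18.8 to 4.0-35.7.

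**The case against.** The strongest reply has four parts.

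- **Other uses of the sample.** A reader might infer that the month 13-15 sample of third-year converters is never used, or is discarded. The documents do not support that. It goes to lipidomics with the rest of the yearly serum. It can be a non-PCOS sample in set A, a pre-onset partner in set B and a point in the time pattern of set C. It is absent only as a predictor in the ROC.
- **Pooling.** A reader might infer that the two lead times are definitely mixed. The wording permits pooling but equally permits one ROC per visit. The conditional split into discovery cases (up to the second year) and validation cases (the rest) already separates the two groups of converters. So the leads may be pooled; it is not stated that they are.
- **A legitimate question.** Prediction from one entry sample is the screening use described in the background and in section 1.1.3, and it contradicts nothing. Imminent risk is an aspiration in item 16, not one of the three aims. This stands, and it rules out replacing the baseline ROC.
- **Detail for an analysis plan.** Horizon and risk-set definitions are often fixed in a SAP, and none is shown here. This weakens the point about the horizon alone. It does not answer the rest, because the protocol itself names the predictor sample and the other pre-diagnosis sample is not part of it.

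**Conclusion.** The point holds in a limited form. The protocol's onset-prediction ROC names baseline abundance only and fixes no horizon. Leads of about 12 and about 24 months may therefore be pooled, and a planned PCOS-free sample about 12 months before third-year diagnoses is not a predictor.

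The weakness remains under either reading. If the visits are pooled, nearly half of the cases (47-50%) carry the long lead. If they are kept apart, only second-year converters inform the 12-month horizon, when about twice as many cases could do so.

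The sizes rest on assumed PCOS at entry, constant annual conversion, no dropout and an assumed AUC of 0.75. The pooled AUCs of 0.65 and 0.70 are illustrations; nothing in the protocol shows that a lipid signal is confined to the last year before diagnosis.

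**What to change.** In the Data mining text of section 1.4:

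1. Keep the baseline ROC, but report it separately for diagnosis at months 13-15 (lead about 12 months) and at months 25-27 (lead about 24 months).
2. Add a 12-month-lead ROC using each converter's last PCOS-free sample: baseline for those diagnosed at months 13-15, the month 13-15 sample for those diagnosed at months 25-27. Compare it with women PCOS-free at that visit and at the next. Use a variance that allows for women who are controls twice, and for third-year converters, who are controls in the first interval and cases in the second. A bootstrap that resamples women would do this.
3. Where the discovery/validation split applies, also report the month 13-15 ROC in third-year converters alone, so that validation cases stay apart from discovery cases. Say whether their month 13-15 samples had served as non-PCOS samples in set A.

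The cost is a little more analysis, using only visits, samples and assays already planned. The visit-specific AUCs will be imprecise: about 7 to 8 cases each under the assumptions above, with standard errors near 0.10 at an AUC of 0.75. They should be reported with confidence intervals and read accordingly.
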